# 2.5 Secondary Endpoints:

Endpoints that support the secondary objectives are listed below. Further description is provided in 5.3 and 9.5.

- Incontinence Quality of Life score (I-QoL)
- Pads per Day
- Urge Incontinence Episodes without a Leak
- Urge Incontinence Episodes with a Leak
- Bathroom Visits per Day
- Nighttime Bathroom Visits
- Usability Data (e.g. Ease of Use, Satisfaction, Preferred Intensity Settings)
- Treatment Compliance

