#### Recruitment

\* During the baseline week subjects will be excluded if they average less than 1 urge incontinence episode per day (with or without a leak).

- Ads placed in social media and other forums to attract candidates to a website that describes the study. These ads will be places in the US without regional geographic targeting and use key words including "incontinence" and "bladder leaks"
- Email to a list of women with urge incontinence who had previously expressed interest in participating in a clinical study.
- Alternately, healthcare providers who become familiar with the study can direct candidates
  to the study. These candidates will go through the same screening as all candidates and
  the referring healthcare provider would not be considered a study investigator. It is
  permissible for the referring healthcare provider to assist the candidates with completion
  of screening/consent information and to forward the information to Elidah.
- TR-1155-FORM-14 identifies the language that will be used in recruitment messaging.

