# 9.5 Data Analyses

This is not a hypothesis driven study. Descriptive statistics will be the primary means of data analysis. Comparison between the treatment groups may be made to, in part, support Elidah's selection of a preferred configuration for eventual product commercialization. However, this case series study is not designed to allow rigorous statistical analysis between the groups.

Electrical stimulation is known to have a positive effect on both UUI, and some women have difficulty distinguishing between UUI and SUI episodes. Accordingly, in an effort accurately capture the totality any therapeutic improvement, the study's **primary outcome measure** of efficacy is a change in total urinary incontinence (UI) leaks, both SUI and UUI. Each adherent subject's Daily Log will be used to determine the average number of urinary incontinence episodes per day for the baseline and 6th week (see 5.5 regarding subject adherence). To accommodate the likelihood that some subjects will omit log data, the "weeks" referred to in the baseline and 6th week assessments refer to the first and last 5 entries in the Daily Log. The percent reduction in UI episodes is then calculated for each patient by subtracting the final week average from the baseline average, dividing the difference by the baseline average, and multiplying by 100. The percent reductions for each patient are then used to define an average (and standard deviation) reduction for each treatment group.

UI episodes per day data may additionally be reported as a responder rate. FDA guidance suggests that subjects with a percent reduction of  $\geq$ 50% be considered responders. Accordingly, the responder rate for each treatment group will be calculated by dividing the number of subjects with a reduction of  $\geq$ 50% by the total number of subjects.

**Secondary outcome measures** will similarly use descriptive statistics (e.g. mean, standard deviation) to characterize changes from baseline. Additionally, where applicable, FDA suggested response rate thresholds will be referenced. Notes on specific secondary outcome measures include:

- Change in urgency episodes with a leak UUI leak data will be analyzed in the same manner as the primary outcome measure data.

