- Change in urgency episodes without a leak Differences in mobility, activity, etc. may impact whether a subject can get to a toilet before an urgency leak occurs. Analysis of episodes without leaks will occur in the same manner as the "with leak" data.
- Change in pad use Reduction in pad usage will be assessed as a percent change relative to the baseline, and as a response rate, wherein a 50% reduction is considered clinically significant. Subjects who do not use a pad during the baseline week will be excluded from the analysis.
- Change in daily bathroom visits / Change in nighttime bathroom visits Descriptive statistics as defined above.
- I-QoL Incontinence Quality of Life scores will be analyzed with respect to a change from baseline. Responders will be those with an I-QoL score increase of 2.5 points, which is defined in the FDA guidance as clinically significant.

Usability surveys will solicit subject feedback pertaining to their experience with the product. Appropriate statistical methods will be used in reporting these subjective measures.

In addition to characterizing outcome measures as a change in value/score (i.e. percent reduction) or a clinically meaningful response (e.g. ≥50% change), post hoc analyses may investigate outcome measures using analysis of covariance (ANCOVA), wherein baseline values are modeled as covariates, which has the advantage of accounting for variation in the magnitude

of the baseline. Additional post hoc ANCOVA may be performed with covariates including age, type of incontinence, BMI or other potentially relevant variables.

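### Urgency episodes without a leak are scored alone as a percent reduction, so a woman whose wet episodes become dry can be scored as worse on this one secondary endpoint

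*Combined protocol and SAP*

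**What the plan says.** Section 2.5 lists "Urge Incontinence Episodes without a Leak" as a secondary endpoint, separate from urge episodes with a leak. It lists no endpoint that adds the two.

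Section 9.5 fixes the analysis through a chain of references:

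- For dry episodes: "Analysis of episodes without leaks will occur in the same manner as the" with-leak data.
- For with-leak episodes: "UUI leak data will be analyzed in the same manner as the primary outcome measure data".
- For the primary outcome, the per-patient percent reduction is found by "subtracting the final week average from the baseline average, dividing the difference by the baseline average, and multiplying by 100". The averages come from the first and last five Daily Log entries, and each group is summarised by mean and standard deviation.
- A responder rate may be added: "the responder rate for each treatment group will be calculated by dividing the number of subjects with a reduction of" 50% or more by the total number of subjects. For secondary measures, such thresholds are to be used where they apply.

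The dry-episode bullet notes that a woman's mobility, activity and similar factors "may impact whether a subject can get to a toilet before an urgency leak occurs". For pad use, Section 9.5 has a zero-baseline rule: "Subjects who do not use a pad during the baseline week will be excluded from the analysis". It gives none for dry episodes. Wet and dry urgency are combined in only one place, the baseline eligibility footnote, which excludes women "if they average less than 1 urge incontinence episode per day (with or without a leak").

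**The concern.** Under the inherited formula, a fall in the dry count is the only movement that scores as benefit. Yet wet and dry are two endings of the same urgency event. If treatment lets a woman reach the toilet in time without abolishing the urge, a wet episode leaves the with-leak count and enters the dry count. The first change is scored as improvement and the second as deterioration, although they are the same clinical event.

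The endpoint therefore has no fixed direction when read alone. Section 2.3 says that differences between groups may inform the choice of configuration, and Section 2.4 says that secondary data may support marketing claims. A configuration that stops leaks better but leaves urgency in place could look inferior here. There is also a computational gap: a percent reduction needs a baseline above zero, and a small baseline produces extreme values that can dominate the mean in a group of 20.

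**Working it through.** The plan states no figure for this endpoint, so there is none to reproduce. The check applies the Section 9.5 formula. All episode counts are assumptions, because the documents give no wet/dry split.

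**Formula.** Percent reduction = 100 × (baseline − final) / baseline. Positive means fewer episodes.

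**When the dry score turns negative.** Final dry = baseline dry − dry episodes resolved + wet episodes that became dry. Hence dry reduction = 100 × (resolved − newly dry) / baseline dry. It is negative exactly when newly dry episodes outnumber those resolved.

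**Examples per day.** For wet 3 to 1 and dry 1 to 2: wet = 100 × (3 − 1)/3 = 66.7%; dry = 100 × (1 − 2)/1 = −100%; total = 100 × (4 − 3)/4 = 25%. Others by the same formula:

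| Baseline wet, dry | Final wet, dry | Wet reduction | Dry reduction | Total reduction |
|---|---|---|---|---|
| 3, 2 | 1, 4 | 66.7% | −100% | 0% |
| 3, 1 | 1, 2 | 66.7% | −100% | 25% |
| 3, 2 | 1, 3 | 66.7% | −50% | 20% |
| 3, 2 | 1, 2 | 66.7% | 0% | 40% |
| 3, 2 | 1, 1 | 66.7% | +50% | 60% |

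The wet result is the same in every row, while the dry score runs from −100% to +50%.

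**Same effect, different mix.** Suppose half of wet episodes become dry and all urgency then falls by 20%.

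- Baseline wet 2, dry 1: wet = 1 × 0.8 = 0.8 (60% reduction); dry = 2 × 0.8 = 1.6 (−60%); total 3 to 2.4 (20%).
- Baseline wet 1, dry 2: wet = 0.5 × 0.8 = 0.4 (60%); dry = 2.5 × 0.8 = 2.0 (0%); total 3 to 2.4 (20%).

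The dry score differs by 60 points for the same assumed effect. The wet and total scores do not differ.

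**Group level.** Ten women with wet 3 to 1 and dry 1 to 3 score −200% on dry; ten whose dry count halves from 2 to 1 score +50%. The group mean is (10 × −200 + 10 × 50)/20 = −75%, SD 128, although the first ten each had 67% fewer urgency leaks.

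**Small baseline.** One dry episode in five entries is 0.2 per day. Wet 3 to 1 with dry 0.2 to 2.2 gives 100 × (0.2 − 2.2)/0.2 = −1000%. In a group of 20, that woman alone contributes −1000/20 = −50 points to the mean.

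**Zero baseline.** Assuming Poisson counts, P(no dry episode in five entries) = exp(−5 × rate). The expected number is out of 20 women.

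| Assumed dry rate per day | P(undefined) | Expected of 20 |
|---|---|---|
| 0.2 | exp(−1) = 37% | 7.4 |
| 0.5 | exp(−2.5) = 8% | 1.6 |
| 1 | exp(−5) = 0.7% | 0.1 |

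**The case against.** The strongest reply is that fewer urgency episodes, dry ones included, is a sensible aim for a device meant to act on urge symptoms, and that the dry count is to be read beside its with-leak partner. Several parts of this stand.

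- A reader might infer that the trial records a woman whose wet episodes become dry as getting worse. It does not. She improves on urgency episodes with a leak and, unless stress leaks offset the gain, on the primary outcome of total leaks. Only one listed secondary endpoint can move the other way.
- The reversal is conditional. If enough of the original dry episodes resolve, the dry score is zero or positive.
- That treatment converts wet to dry is an inference. The plan attributes reaching the toilet to mobility, activity and the like, which are not treatment effects.
- The responder rate is optional for this endpoint, not mandated.
- The size of the zero-baseline problem is unknown: 37% and 0.7% both come from assumed rates.
- The study is descriptive, with no rigorous between-group test intended. No error rate or sample size is affected, and the anticipated clearance criteria in Section 9.1 rest on leaks per day.

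What the reply does not answer is that no listed outcome counts urgency as a whole. Bathroom visits are not limited to urgency episodes. The post hoc ANCOVA in Section 9.5 still takes the dry count alone as its outcome. Reading separate wet and dry mean percents side by side does not recover the total, because each has a different denominator for each woman.

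**Conclusion.** The point holds as a limited one about interpretability. As planned, the dry-urgency percent reduction can score a wet-to-dry shift as worsening, and it does so whenever newly dry episodes outnumber the dry episodes that resolve. In the assumed examples with a two-thirds fall in leaks tabulated above, the dry score ranges from −100% to +50%. Which sign would dominate cannot be predicted, because the wet/dry mix is not given. The formula also fails for a woman with no dry episode in her first five entries, and the plan has a rule for this only for pads.

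A reader might go further and call the endpoint uninterpretable. The documents do not support that: it cannot be interpreted alone, but the with-leak results are reported too, and the total can be built from the same counts. The primary outcome and the overall efficacy conclusion are untouched. The conclusion about direction rests on the formula. The magnitudes rest on assumed counts and on the Poisson assumption.

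**What to change.** In Sections 2.5 and 9.5, add change in total urgency episodes per day (with plus without a leak) as the urgency outcome, analysed by the plan's existing percent-reduction method. A pure wet-to-dry shift then scores 0%, and a real fall in urgency scores as benefit. Its denominator is also safer: a woman who meets the eligibility footnote has at least 7 urgency episodes over a complete seven-day baseline, so a zero in the first five entries would need all of them to fall in the last two days.

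Report dry episodes beside it as mean per day and absolute change, with no percent reduction and no responder rate. This also removes the need for a zero-baseline rule on that endpoint.

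If the share of urgency episodes that leak is reported as well, compute it at group level or state how women with no urgency episodes at week 6 are counted. Otherwise it is 0/0 for those with the best result.

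The cost is a wording change and one extra descriptive summary. The Daily Log form is not among the documents, but the two listed endpoints already require separate wet and dry counts, so the total should need no new data.

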# 9.6 Data Pooling

This study is, in part, being conducted to provide scientific evidence to support FDA clearance of the ELITONE-UUI device. Elidah may pool data from both treatment groups if there is demonstrated homogeneity between the subject groups and the outcome measures.

#### 10. DATA COLLECTION AND QUALITY ASSURANCE

#### 10.1 Data Collection Forms

Subjects will provide data using the following forms:

- Pre-Study Questionnaire (TR-1155-FORM-1)
- I-QoL Questionnaire (TR-1155-FORM-2)
- Daily Log (TR-1155-FORM-3)
- Post-Study Questionnaire (TR-1155-FORM-4)

The forms are sent to the subjects in hardcopy and subjects return the completed forms to Elidah in envelopes with pre-paid postage. Returned forms are identified by the subject's ID Number and stored in the corresponding subject folder in the study binders. Electronic equivalents may also be utilized.

# 10.2 Materials Management

In addition to the items described in 10.1, at the beginning of the study each subject will receive the following:

- ELITONE-UUI controller and ELITONE accessories (see 6.4)
- ELITONE electrodes (see 6.3)
- User Manual (TR-1155-FORM-12)
- Pre-paid postage and packaging

Upon completion of the study, subjects are required to return the controller so that study staff can download saved treatment data. Elidah will reconcile components on the Case Report Form (TR-1155-FORM-10). After the controller is inspected it will be returned to the subject.

## 10.3 Specimen Management

No biological specimens are collected as part of this study

## 10.4 Data Management

All subject folders and study binders will be kept in a locked cabinet at Elidah.

Data from the forms will be transferred to electronic formats (e.g. Excel) for analysis, but only in formats that do not include identifying subject data. This data may be generally accessible to Elidah staff and included in formal test reports within Elidah's Quality Management System.

Subject identifying data may be converted to an electronic format, but will not be generally

accessible to Elidah staff.

In accordance with HIPPA requirements, at the conclusion of the study all study binders (or equivalent electronic files) will be maintained under lock and key for a minimum of seven years after last patient participation.

## 10.5 Data and Safety Monitoring Plan

Elidah will identify a Clinical Director who will be responsible for managing the study and ensuring that the rights and well-being of human subjects are protected, that the reported data are accurate and complete and verifiable from source documents, and that the conduct of the trial is in compliance with the approved protocol, with good clinical practice, and with applicable regulatory requirements. Specific responsibilities of the Clinical Director include:

- Verify that equipment and staff are adequate to safely and properly conduct the study
- Verify that subjects:
  - Meet eligibility requirements
  - o Provided informed consent prior to enrollment
  - Are adequately informed about the device use, study requirements and risks of participation
  - Receive all necessary study materials
  - Return all the required data collection forms and specimens
- Verify that, with respect to the device:
  - That shelf-life and storage conditions meet requirements (as applicable)
  - o Sufficient supplies (i.e. electrodes, controllers) are sufficient to complete the study
  - o That the device is provided only to eligible subjects
  - o That the receipt, use, and return of the device is controlled and complies with applicable regulation.
- Verify that source documents and data analyses are accurate and complete
- Verify that adverse events are appropriately reported
- Verify that protocol deviations are appropriately reported

In addition, a Data Safety and Monitoring Board will be established which will review study compliance and adverse events. The Data Safety and Monitoring Board will comprise, at a minimum, the Clinical Director, an individual responsible for technological aspects of the device and an individual with medical training relevant to the used of the device.

EMS and TENS devices (including the ELITONE device) are sold over the counter and used in an at-home environment. Given the high degree of similarity between those devices and the ELITONE-UUI device, the described level of monitoring is considered appropriate for the low level of risk (see 7).

## 10.6 Quality Assurance

Training –The Clinical Director is responsible for ensuring that the study staff can perform
the responsibilities they have been assigned. All study staff will be required to complete
the NIH Protection of Human Subjects Training before performing any function of the
study.

- Quality Control Committee Given to the small scope of the study, a Quality Control
  Committee will not be utilized. The Clinical Director has responsibility pertaining to
  maintenance of study quality, and the Data Safety and Monitoring Board exists to ensure
  appropriate human protection regulations are met and adverse events are appropriately
  handled.
- Metrics Section 9.5 defines that data analysis and statistical approach used to determine study success. Upon completion of the analysis one or more persons not involved with the original data analysis will audit the data entry, mathematical calculations and statistically driven conclusions.
- **Protocol Deviations** Protocol deviations will be documented using Protocol Deviation Log (TR-1155-FORM-8) and retained within the Study Binders. The Clinical Director and/or Data Safety and Monitoring Board will make the determination of whether the impact of the deviation should be considered in subsequent analysis.

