# 5.7 Blinding

Subjects will be blinded to the treatment group. Study staff will not be blinded to the treatment group. This is done to enable staff to respond to questions regarding the timing (i.e. on/off cycles) of the stimulation, which is treatment group specific. See 9.3 for addition discussion of blinding.

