## 7.4 Reporting Procedures

Subjects are instructed to report adverse events at the time of occurrence via either phone or email. Adverse events may also be identified during routine communication with the subject or review of the subject's Daily Log.

The Data Safety and Monitoring Board will use the following 0 to 5 scale to grade adverse events (AE): 0 = none or event is not clinically significant, 1 = mild AE that does not require treatment, 2 = moderate AE that does require treatment, but resolves completely, 3 = severe AE (e.g. one that results in temporary inability to conduct one or more everyday activities and requires ongoing medical attention), 4 = life threatening or results in permanent inability to conduct one or more everyday activities, and 5 = death.

In the event of an AE rated ≥2 the Clinical Director will instruct the subject to obtain medical treatment from a qualified healthcare professional. If the subject becomes ill or is physically injured due to the use of the ELITONE-UUI device, she will not be responsible for the costs required to diagnose or treat such injury. The costs of diagnosis and medical care for any complication, injury, or illness caused by the study device or properly performed non-standard of care investigational procedure required by the study will be covered by Elidah, as long as the subject has followed the study protocol. The subject will not lose any of her legal rights and she does not release Elidah and the study staff from liability for mistakes or intentional misconduct by participating in the study.

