# 9.3 Blinding

The instructional materials provided to each subject will include a brief description of the waveform (e.g. 4 seconds with one stimulation, followed by 4 seconds of a slightly different stimulation, followed by 6 seconds of rest), which aides is establishing expectations of proper function and identification of a suitable treatment intensity. Accordingly, the subjects and staff members interacting with those subjects are not considered to be blinded.

Study personnel responsible for post-treatment data analysis will be blinded from the group assignment during analysis of individual subject data. For example, baseline and 6th week episodes/day calculations and pad weight measurements will be made for each subject without knowledge of group assignment.

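### Sections 10.6 and 5.5 leave decisions on deviations and non-adherent data to the Clinical Director and/or a board including that person, with no masking or lock, and the analyst blind in 9.3 does not reach them

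*Combined protocol and SAP*

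**What the plan says.** **Who decides.** On deviations, 10.6 states: "The Clinical Director and/or Data Safety and Monitoring Board will make the determination of whether the impact of the deviation should be considered" in later analysis. The wording allows the Clinical Director to decide alone. On non-adherence, 5.5 has the board review each woman's reason during data analysis and settle whether and how her data are adjudicated. Section 9.5 builds the primary measure from adherent women's logs.

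**Who these people are.** Under 10.5, "Elidah will identify a Clinical Director who will be responsible for managing the study". The same section adds: "The Data Safety and Monitoring Board will comprise, at a minimum, the Clinical Director", together with a person responsible for the device technology and a person with relevant medical training.

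**What is masked.** Section 9.3 states: "Study personnel responsible for post-treatment data analysis will be blinded from the group assignment during analysis of individual subject data". Its examples are each woman's episodes/day and pad-weight figures. Section 5.7 states: "Study staff will not be blinded to the treatment group". Section 9.3 adds: "Accordingly, the subjects and staff members interacting with those subjects are not considered to be blinded". No section masks the Clinical Director or the board.

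**What the result is used for.** Section 9.1 expects that a mean reduction of at least 50% and/or a responder rate of at least 50% will be enough to support clearance. Section 9.5 allows the groups to be compared to help select a configuration.

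**The concern.** The blind in 9.3 protects the calculation of each woman's percent reduction. It does not protect the choice of which women or data enter the group figures, and that choice is where most of the judgement lies. The plan sets no criteria, deadline or masking for the deviation decision. It places the non-adherence decision at the stage when outcomes are being worked out. Leak data may be visible earlier still: 4.5 has study staff monitoring the digital treatment diary every two weeks, and 10.4 lets de-identified analysis data be generally accessible to sponsor staff.

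Someone following the plan exactly could therefore discount a poor responder's data for a deviation that is passed over in a good responder. Two things are at stake: the within-group figures read against 50%, and the between-group contrast that informs the configuration choice. The study is descriptive with no planned test, so no type I error rate is involved. The risk is bias in the reported estimates.

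**Working it through.** The plan gives no figure on this point, so there is none to reproduce. The check sets the sections side by side and then shows how far such decisions could move a group of 20.

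**Step 1. Do the decision-makers know group?** No sentence says so of the Clinical Director. Four statements point that way:
- 10.5: the Clinical Director manages the study.
- 5.7: study staff are not masked.
- 9.3: staff who interact with subjects are not masked.
- 7.4: for adverse events graded 2 or higher, "the Clinical Director will instruct the subject to obtain medical treatment from a qualified healthcare professional", so this person does interact with subjects.

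Unmasking of the Clinical Director is therefore a strong inference. For the other board members the documents are silent.

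**Step 2. Does the 9.3 blind reach these decisions?** It applies to analysts, to group assignment, and to individual subject data. The decisions in 5.5 and 10.6 are made by other people and concern what enters the group result. The blind does not extend to them.

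**Step 3. Does any other control reach them?** Section 10.6 has a person outside the original analysis audit data entry, calculations and conclusions once the analysis is complete. Exclusions and masking are not mentioned.

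**Step 4. Possible size.** Inputs: 20 women per group (5.2) and the 50% benchmark (9.1). Assumptions: k non-responders are set aside and leave the denominator. Both k and the starting counts are illustrative.

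- Responder rate = r/(20 − k). With r = 9: 9/20 = 45.0%; with k = 2, 9/18 = 50.0%. With r = 8: 8/20 = 40.0%; with k = 4, 8/16 = 50.0%.
- Mean reduction, if the k women had 0% change = 20 × m/(20 − k). With m = 45% and k = 2: 900/18 = 50.0%.
- Chance of showing at least 50% when the true responder rate is 40% = P(X ≥ r*), with X binomial (20, 0.40) and r* the smallest r for which r/(20 − k) ≥ 0.5:

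| k | r* | Chance |
|---|---|---|
| 0 | 10 | 24.5% |
| 2 | 9 | 40.4% |
| 4 | 8 | 58.4% |

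These three results need knowledge of outcome only. They would be the same if group were fully masked.

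- Between-group gap, starting from 10/20 in each group, with k non-responders set aside in one group only = 10/(20 − k) − 10/20. With k = 2: 55.6% − 50.0% = 5.6 points. With k = 4: 62.5% − 50.0% = 12.5 points. Favouring one configuration in this way requires knowledge of group as well as outcome.

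**The case against.** The strongest reply is that 9.3 never claims more than it delivers. It says openly that subjects and the staff who deal with them are not blinded, and it masks a step that is not trivial, since logs have gaps, five entries must be selected at each end, and some women extend treatment. The study is descriptive, 9.1's 50% is an expectation and not a tested criterion, and 10.6 includes an independent audit. This stands as far as it goes: the blind has value within its scope, and no formal error rate is at risk. It does not supply the missing control, because the audit comes after the analysis and does not mention who was left out.

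Several stronger readings are tempting, but the documents do not support them:

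- *The Clinical Director and board are stated to be unmasked.* For the Clinical Director this is inferred; for the other members nothing is stated.
- *Illness, new medication, extended treatment and missed sessions all give free latitude as deviations.* Section 5.4 and Table 5-1 provide for extension when week 6 falls in illness or menses, 5.6 allows medically necessary new medication if recorded, and 5.5 sets a threshold of 20 of 30 sessions. The documents give no expected number of deviations.
- *Section 10.6 authorises removing women.* It speaks of considering a deviation's impact, which could mean a note or a sensitivity analysis. Section 9.5 divides responders by all subjects without defining that total.
- *The move from 45% to 50% measures a weakness in the group blind.* It does not; it arises from knowing outcome.

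**Conclusion.** The concern holds in this form: 5.5 and 10.6 grant discretion over what enters the analysis without requiring masking to group or outcome, or a decision before results are known, and the masking in 9.3 does not extend to that discretion. This is more than missing detail, because the rule as written permits outcome-aware selection, and 5.5 places its decision during the analysis.

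With 20 women per group, two decisions are enough to carry a 45% responder rate, or a 45% mean reduction, to the 50% benchmark. That size rests on two women being set aside, both being non-responders (with 0% change in the case of the mean), and both leaving the denominator. The starting values were chosen to show how few decisions would be needed; they do not predict what will happen. A reader might go on to infer that the blind is worthless or that selective exclusion is intended. The documents support neither. The point is that the plan does not prevent it, and that masking to group alone would not protect the within-group figures.

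**What to change.** Amend 5.5, 9.3 and 10.6 together; changing only 9.3 and 10.6 would leave the more explicit route in 5.5 open.

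- Make every deviation or non-adherence decision that affects the analysis from a listing that omits group, waveform details and leak counts.
- Make the listing complete, covering every logged deviation and every woman below the adherence requirement, so that discretion does not move to whoever prepares it.
- Date and lock the decisions before any week-6 episodes/day value is calculated, and unmask only after the lock.
- Report the primary mean reduction and responder rate with and without the women set aside under these rules, stating the denominator each time.

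The cost is protocol wording, one masked listing for about 40 to 55 women (5.2), and a short delay before analysis. Treatment, sample size and subject contact do not change. Masking will be imperfect: a study manager who verifies source documents under 10.5 may recall individual women and their logs. The with-and-without report offsets this, because it shows how far the decisions moved the result.
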